## 10.3 Responsibilities of the investigator and IRB/IEC

Before initiating a trial, the investigator/institution must obtain approval/favorable opinion from the Institutional Review Board/Independent Ethics Committee (IRB/IEC) for the trial protocol, informed consent form, consent form updates, patient recruitment procedures (e.g., advertisements) and any other written information to be provided to patients/patients. Prior to study start, the investigator is required to sign a protocol signature page confirming his/her agreement to conduct the study in accordance with these documents and all of the instructions and procedures found in this protocol and to give access to all relevant data and records to Novartis monitors, auditors, Novartis Quality Assurance representatives, designated agents of Novartis, IRBs/IECs, and regulatory authorities as required. If an inspection of the clinical site is requested by a regulatory authority, the investigator must inform Novartis immediately that this request has been made.

## **10.4 Publication of study protocol and results**

The key design elements of this protocol will be posted in a publicly accessible database such as clinicaltrials.gov. In addition, upon study completion and finalization of the study report the results of this trial will be either submitted for publication and/or posted in a publicly accessible database of clinical trial results.

## **10.5 Quality Control and Quality Assurance**

Novartis maintains a robust Quality Management (QM) system that includes all activities involved in quality assurance and quality control, including the assignment of roles and responsibilities, the reporting of results, and the documentation of actions and escalation of issues identified during the review of quality metrics, incidents, audits and inspections.

Audits of investigator sites, vendors, and Novartis systems are performed by Novartis Pharma Auditing and Compliance Quality Assurance, a group independent from those involved in conducting, monitoring or performing quality control of the clinical trial. The clinical audit process uses a knowledge/risk based approach.

Audits are conducted to assess GCP compliance with global and local regulatory requirements, protocols and internal SOPs, and are performed according to written Novartis processes.

# **11 Protocol adherence**

This protocol defines the study objectives, the study procedures and the data to be collected on study participants. Additional assessments required to ensure safety of patients should be administered as deemed necessary on a case by case basis. Under no circumstances including incidental collection is an investigator allowed to collect additional data or conduct any additional procedures for any purpose involving any investigational drugs under the protocol, other than the purpose of the study. If despite this interdiction, data, information, observation would be incidentally collected, the investigator shall immediately disclose it to Novartis and not use it for any purpose other than the study, except for the appropriate monitoring on study participants.

Investigators ascertain they will apply due diligence to avoid protocol deviations. If an investigator feels a protocol deviation would improve the conduct of the study this must be considered a protocol amendment, and unless such an amendment is agreed upon by Novartis and approved by the IRB/IEC and health authorities, where required, it cannot be implemented.

## **11.1 Protocol amendments**

Any change or addition to the protocol can only be made in a written protocol amendment that must be approved by Novartis, health authorities where required, and the IRB/IEC prior to implementation. Only amendments that are intended to eliminate an apparent immediate hazard to patients may be implemented immediately provided the health authorities are subsequently notified by protocol amendment and the reviewing IRB/IEC is notified. Notwithstanding the need for approval of formal protocol amendments, the investigator is

expected to take any immediate action required for the safety of any patient included in this study, even if this action represents a deviation from the protocol. In such cases, the reporting requirements identified in [Section 7](#) must be followed.

## 13 Appendix 1: Clinically notable laboratory values and vital signs

The following criteria will be used to define expanded limits and notable abnormalities of key laboratory tests.

Clinically notable values will be forwarded to Novartis/CRO at the same time that they are sent to investigators. Any action based on these laboratory values should be discussed with Novartis/CRO personnel.

**Table 13-1 Safety Analyses: Expanded Limits and Notable Criteria**

Laboratory Variable	Final Harmonization	
	Notable Criteria	SI Units
	Standard Units	
LIVER FUNCTION AND RELATED VARIABLES		
SGOT (AST)	> 3 x ULN	> 3 x ULN
SGPT (ALT)	> 3 x ULN	> 3 x ULN
Bilirubin	> 2 x ULN	> 2 x ULN
Alkaline phosphatase	> 2.5 x ULN	> 2.5 x ULN
RENAL FUNCTION, METABOLIC AND ELECTROLYTE VARIABLES		
Creatinine (serum)	> 2 x ULN	> 2 x ULN
HEMATOLOGY VARIABLES		
Hemoglobin	20 g/L decrease from baseline	
Platelet Count	< 100 x 10E9/L	
White blood cell count	< 0.8 x LLN	
Neutrophils	< 0.9 x LLN

MCS Mental Component Summary

MedDRA Medical Dictionary for Drug Regulatory Affairs

MTX Methotrexate

OR Odds ratio

PCS Physical Component Summary

PD Pharmacodynamics PFS Prefilled syringe

PGA Patient's Global Assessment
PhGA Physician's Global Assessment

Novartis For business use only Page 7 of 53 SAP Amendment 1 CAIN457ADE11C

PMR Polymyalgia rheumatica

PPS Per-Protocol Set

PRO Patient-reported Outcomes

PT Preferred term

qd Qua'que di'e / once a day

QoL Quality of Life

RAP Report and Analysis Process
RAS Randomized Analysis Set

RD Risk difference RR Risk ratio

SAE Serious Adverse Event SAP Statistical Analysis Plan

s.c. SubcutaneousSD Standard DeviationSF-36 Short Form 36

SOC System Organ Class

SOP Standard Operating Procedure

TEAE Treatment Emergent Adverse Event

TFLs Tables, Figures, Listings
VAS Visual Analog Scale

WHO World Health Organization

1 Introduction

This Statistical Analysis Plan (SAP) describes the statistical analysis for the clinical study report (CSR) for CAIN457ADE11C according to Section 9 of the study protocol (version no. 3 including Amendment 3) along with any additional analyses, specifications or deviations from this protocol planned before unmasking of the data. Determination of the sample size is specified in Section 3.

This document is written in the future tense. The CSR results will be used to provide information to support a phase III program of secukinumab in patients with giant cell arteritis (GCA).

The following documents were used to support the creation of this SAP:

[figure not shown]
- Study protocol (version no. 3 including Amendment 3)
- Case report forms (CRFs) (version 9)
- AIN457 efficacy master analysis plan (MAP) M3 Amendment 5
- AIN457 safety master analysis plan (MAP) M3 Amendment 5

1.1 Study design

This is a randomized, parallel-group, double-blind, placebo-controlled, multicenter, phase II study designed to evaluate the efficacy of secukinumab compared to placebo in combination with a 26-week prednisolone taper regimen in terms of sustained remission in patients with newly diagnosed or relapsing GCA who are naïve to biological therapy.

The study will consist of 6-week (maximum duration) screening period, a 52-week treatment period and an 8-week safety follow-up period (Figure 1-1).

Figure 1-1 Study design

Patients who do not achieve remission by Week 12, experience a flare after remission or cannot adhere to the prednisolone taper regimen will enter "escape". Upon entering "escape", patients will receive prednisolone at a dose determined by the physician's clinical judgment and continue to receive secukinumab or placebo in a blinded manner. Patients in "escape" should continue to attend all subsequent scheduled visit assessments.

As outlined in the protocol, most flares occurred within the first 6 months in the GiACTA trial (Stone et al 2017). Therefore, the time point for the primary analysis of this study is at Week 28, to evaluate the effect of secukinumab in patients who are on study treatment or placebo for 24 weeks.

At the randomization visit (Baseline) all eligible patients will be given a randomization number that assigns them to one of the following 2 arms in a 1:1 ratio:

- Group 1: secukinumab 300 mg s.c. + 26-week prednisolone taper regimen
- Group 2: placebo s.c. + 26-week prednisolone taper regimen

The patient randomization list was produced by or under the responsibility of Novartis Biometry using a validated system ensuring assignment of treatment arms to randomization numbers in the specified ratio. The randomization scheme was reviewed and approved by a member or delegate of the Novartis Biometry Randomization Group. It is planned to randomize at least 25 patients per treatment group.

Patients will receive secukinumab/placebo at Baseline, Week 1, 2, 3, 4, then every 4 weeks thereafter through to Week 48 (last dose) at the study center. Assessments will be performed in accordance to the study schedule. Patients in both groups will follow the protocol-defined prednisolone taper regimen.

In total, three interim analyses (IAs) will be conducted unless deemed unwarranted by the study team:

- First interim analysis (IA1): after approximately 50% of patients reach Week 28
- Second interim analysis (IA2): after approximately 50% of patients reach Week 52
- Third interim analysis (IA3): 100% of patients reach Week 28

The analyses for each of the aforementioned IAs are detailed in separate SAPs.

1.2 Study objectives and endpoints

The following table (Table 1-1) is an overview of the study objectives and endpoints.

Table 1-1 Study objectives and endpoints

	Objective	Endpoint	
Primary	 To evaluate the efficacy of secukinumab compared to placebo, in combination with a 26- week prednisolone taper regimen, based on the proportion of patients with GCA who have sustained remission. 	 Proportion of GCA patients in sustained remission at Week 28 	

Endpoint Objective To evaluate the efficacy of Remission rate at Week 12 Secondary secukinumab in combination with Time to first GCA flare after Baseline a 26-week prednisolone taper (up to Week 52) regimen versus placebo in patients with GCA, measured by the following: Remission rate at Week 12 Time to first flare after remission Cumulative corticosteroid dose up Total cumulative prednisolone dose to Week 28 and up to Week 52 over 28 weeks and 52 weeks Proportion of patients with GCA Proportion of GCA patients in who have sustained remission sustained remission at Week 52 Proportion of patients on prednisolone Proportion of patients on dose ≤ 5mg/day at Week 19, 28 and prednisolone dose ≤ 5mg/day at Week 19, 28, 52 Changes from baseline in disease Changes from Baseline in disease activity and quality of life measures at activity and quality of life measures at Week 4, 8, 12, 16, Week 4, 8, 12, 16, 20, 24, 28, 36, 44 20, 24, 28, 36, 44 and 52 for each and 52 for each of the following: of the following: Physician's Global Assessment PhGA, VAS (PhGA), Visual Analog Scale (VAS) Patient-reported outcomes (PROs) **PROs** Patient's Global Assessment PGA, VAS (PGA), VAS **FACIT-Fatigue** Functional Assessment of SF-36 Chronic Illness Therapy EQ-5D Fatigue Score (FACIT-Fatigue) Short Form 36 (SF-36) EuroQoL-5D (EQ-5D) Laboratory parameters Change from Baseline in CRP and (Baseline vs. Week 28 and 52): ESR at Week 4, 8, 12, 16, 20, 24, 28, 32, 36, 40, 44, 48, 52 C-reactive protein (CRP) Ervthrocyte sedimentation rate (ESR) To evaluate the safety/ tolerability Safety and tolerability assessments and immunogenicity of over time: incidence and severity of secukinumab in patients with adverse events (AEs) and serious AEs newly diagnosed or relapsing GCA (SAEs)

2 Statistical methods

2.1 Data analysis general information

This study will be conducted under the sponsorship of Novartis. The analysis will be performed by Novartis NBS CONEXTS or a designated contract research organization (CRO) (if applicable).

All analyses will be performed using SAS® statistical software (Version 9.4 or a more recent version), unless otherwise noted.

The independent statistical and statistical programming team will perform the unblinded statistical analyses. These analyses are detailed in the respective data monitoring committee (DMC) and IA SAPs.

Data will be summarized with respect to demographic and other baseline characteristics along with safety observations.

Descriptive statistics (the number of non-missing observations [n], mean, median, standard deviation [SD], minimum, and maximum values) will be presented for continuous variables.

For categorical variables, the number and percentage of each category within a variable will be calculated for non-missing data. If a count of zero is obtained for categorical data, only the zero count will be displayed. If no treatment group satisfies a category, then the category will be

displayed, unless stated otherwise. A row (category) denoted 'Missing' will be included in count tabulations if a non-zero count of missing values is present. In addition, the corresponding percentage for this row will be displayed.

All data will be listed by center and subject number, unless otherwise stated.

It is planned that the data from all centers that participate in this study will be used so that an adequate number of patients will be available for analysis.

2.1.1 General definitions

2.1.1.1 Treatment

Study treatment

At Baseline, patients will be assigned to one of the following two arms in a 1:1 ratio:

- Group 1: secukinumab 300 mg subcutaneous (s.c.) + 26-week prednisolone taper regimen
- Group 2: placebo s.c. + 26-week prednisolone taper regimen

The study treatment is secukinumab 300 mg supplied in prefilled syringes (PFS) each containing 150 mg of secukinumab, or placebo supplied in PFS to match secukinumab dose.

Co-administered treatment

The co-administered treatment refers to prednisolone tablets for tapered oral administration (taper regimen from a dose of 25 mg to 60 mg at Baseline to 0 mg at Week 28). Prednisolone will be supplied as 1 mg, 5 mg, 10 mg, 20 mg tablets.

Note: Prednisolone may continue to be taken after the 26-week prednisolone taper regimen.

2.1.1.2 Date of first administration of treatment

Date of first administration of study treatment

The date of first administration of study treatment is defined as the first date when a non-zero dose of study treatment was administered and recorded on the "Dosage Administration Record-Investigational Product" electronic CRF (eCRF).

Date of first administration of co-administered treatment

The date of first administration of co-administered prednisolone treatment is defined as the first date when a non-missing dose of co-administered prednisolone treatment was administered and recorded on the "Dosage Administration Record-Prednisolone" eCRF.

Note: A patient may have a "0" dose as part of the prednisolone dosing taper regimen.

2.1.1.3 Date of last administration of treatment

Date of last administration of study treatment

The date of last administration of study treatment is defined as the last date when a non-zero dose of study treatment was administered and recorded on the "Dosage Administration Record-Investigational Product" eCRF.

Date of last administration of co-administered treatment

The date of last administration of co-administered prednisolone treatment is defined as the last date when a non-missing dose of co-administered prednisolone treatment was administered and recorded on the "Dosage Administration Record-Prednisolone" eCRF.

Note: A patient may have a "0" dose as part of the prednisolone dosing taper regimen.

2.1.1.4 Safety observation period

The safety observation period (days) for treated patients begins at the first administration of study treatment within this study (refer to Figure 1-1). It finishes at:

- the date of the Month X visit for patients that attend it (for patients who have not discontinued study treatment or study prior to the Month X visit)
- the latest day in the window for the Month X visit for patients who have not discontinued (study treatment or study) prior to the Month X visit but do not attend that visit
- the date of the last visit (including the study discontinuation visit) for patients who have discontinued study treatment prior to the Month X visit

where Month X is the last scheduled visit in the study.

Safety observation period (days) is defined as:

• (date of last administration of study treatment - date of first administration of study treatment) + 85 (i.e. 84 days after last administration of study treatment)

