### 5.6.2 Discontinuation of study treatment

Discontinuation of study treatment for a patient occurs when study treatment is stopped earlier than the protocol planned duration. Discontinuation of study treatment can be decided by either the patient or the investigator.

Study treatment must be discontinued under the following circumstances:

- Patient decision - patients may choose to discontinue study treatment for any reason at any time.
- The investigator believes that continuation would negatively impact the safety of the patient or the risk/benefit ratio of trial participation.
- Emergence of the following AEs:
  - Any severe AE or SAE that is not compatible with administration of study medication, including AEs that require treatment with an unacceptable co-medication
  - Life-threatening infection

- Onset of lymphoproliferative disease or any malignancy except for treated basal cell carcinoma, treated actinic keratosis, treated in situ carcinoma of the cervix, or non-invasive malignant colon polyps which are being or have been removed
- Any protocol deviation that results in a significant risk to the patient's safety.
- Pregnancy (see [Section 6.4.7](#) and [Section 7.1.4](#))
- Use of prohibited treatment as per recommendations in [Section 5.5.8](#).
- AEs, abnormal laboratory values or abnormal test results that indicate a safety risk to the patient.
- Any laboratory abnormalities that in the judgment of the investigator, taking into consideration the patient's overall status, prevents the patient from continuing participation in the study.

If discontinuation of study treatment occurs, the investigator must determine the primary reason for the patient's premature discontinuation of study treatment and record this information on the Dosage Administration CRF.

If study treatment discontinuation occurs because of study treatment unblinding, please refer to [Section 5.5.9](#).

Discontinuation of study treatment does not require the patient to be discontinued from the study and all ongoing visit assessments except in case of withdrawal of informed consent (see [Section 5.6.3](#)). Refer to [Section 6](#) for the visit schedule and assessments.

Patients who prematurely discontinue the study treatment (s.c. secukinumab or placebo) are encouraged to remain in the study to continue the study-related assessments until completion of the study.

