- Prednisolone dose for GCA will be based on the information collected on the "Dosage Administration Record-Prednisolone" eCRF. However as the prednisolone taper regimen is planned to be 26-weeks in duration, the Investigator is not required to enter daily prednisolone records on the "Dosage Administration Record-Prednisolone" eCRF post Week 26 unless the patient has taken additional prednisolone for GCA. Therefore if the patient is still in the study at the post Week 26 week of interest and has no prednisolone information in the "Dosage Administration Record-Prednisolone" eCRF for that week of interest the patient will be regarded as having 0 mg/day at that week of interest.

Descriptive summary statistics for the change as well as relative change from baseline of PhGA VAS to each study visit of interest will be presented for each treatment group. Change from baseline will only be summarized for patients with both baseline and post baseline values.

The analysis of the PRO secondary endpoints is detailed in Section 2.10.

Descriptive summary statistics for the change from baseline of CRP and ESR to each study visit of interest will be presented for each treatment group. Change from baseline will only be summarized for patients with both baseline and post baseline values. Further details are provided in Section 2.8.3. This analysis will also be presented for the following subgroups:

- Sustained remission until Week 28 (Yes, No)
- Sustained remission until Week 52 (Yes, No)

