2.8.3 Laboratory data

Only "on-treatment" laboratory data (i.e. all assessments in the safety observation as defined in Section 2.1.1.4) will be summarized.

The summary of laboratory evaluations will be presented for three groups of laboratory tests (hematology, clinical chemistry, and urinalysis).

Descriptive summary statistics for the change from baseline to each study visit of interest will be presented. These descriptive summaries will be presented by laboratory test and treatment group. Change from baseline will only be summarized for patients with both baseline and post baseline values. In addition, shift tables using the low/normal/high/ (low and high) classification will be used to compare Baseline to the worst on-treatment value.

For urinalysis, frequency tables will be presented.

All laboratory data will be listed by center, subject number, and visit/time and if ranges are available, abnormalities will be flagged.

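### SAP 2.1.1.4 ends the safety observation period in two conflicting ways, so the on-treatment laboratory and vital-sign data of patients who stop injections early but stay in the study are not uniquely defined

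*SAP*

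**What the plan says.** SAP 2.1.1.4 starts the safety observation period at the first dose and then gives its end twice.

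- **Bullets.** Patients who have not discontinued end at the Month X visit, or at the last day of its window if they miss it. Patients who stopped study treatment early end at "the date of the last visit (including the study discontinuation visit) for patients who have discontinued study treatment prior to the Month X visit". Month X is explained in the same place: "where Month X is the last scheduled visit in the study".
- **Formula.** The length is last dose date minus first dose date, plus 85, glossed as "i.e. 84 days after last administration of study treatment".

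No wording joins the two or says which prevails, and SAP section 4 (changes to protocol-specified analyses) is silent.

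The period controls outputs. SAP 2.8.3 restricts the laboratory summaries to "all assessments in the safety observation as defined in Section 2.1.1.4" and builds shift tables from baseline to the worst on-treatment value. SAP 2.8.4.1 applies the same restriction to vital signs.

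Injections are given weekly to Week 4, "then every 4 weeks thereafter through to Week 48 (last dose) at the study center" (SAP 1.1). Protocol 5.6.2 foresees patients who stop early but stay; they "are encouraged to remain in the study to continue the study-related assessments until completion of the study". Protocol 5.5.8 likewise lets patients permanently taken off the injections because of prohibited medication continue assessments to Week 52 and follow-up.

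**The concern.** For a patient who stops injections and stays, the last visit can fall many months after the last dose. The bullets would count everything up to that visit as on-treatment. The formula would stop at 84 days. Two programmers following the same section could therefore produce different tables.

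The shift-to-worst tables are the most exposed, because one late value can set a patient's worst category. Under the bullets, a value taken long after the drug was stopped, possibly on another medication, could be reported as an on-treatment abnormality. Neutropenia is listed as an important identified risk in protocol 3.6, so at least one affected parameter matters. With about 25 patients per arm, one reclassified patient moves a percentage by 1/25 = 4 points.

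**Working it through.** **Inputs.** Nominal study day of week w is 7w + 1, which matches the target days in SAP Table 2-1 (Week 48 = Day 337, Week 60 = Day 421). First dose is Day 1. Post-baseline hematology, chemistry and urinalysis visits in protocol Table 6-1 are Weeks 4, 12, 28, 36, 44 and 52, that is Days 29, 85, 197, 253, 309 and 365.

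**Rules.**

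- Formula end day = (last dose day − 1) + 85.
- Bullet end day = last visit, taken here as Day 421 for a patient who stays to Week 60.

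**Completer, as a check on the plan's own figures.** (337 − 1) + 85 = 421, the Week 60 target day. The two rules agree. The actual Week 60 visit may fall anywhere from Day 408 to Day 435, so they can differ by −13 to +14 days, but no laboratory test is scheduled after Week 52.

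**Early stoppers followed to Week 60, visits at target days.**

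| Last dose | Formula end day | Gap to Day 421 | Laboratory visits after the formula end |
|---|---|---|---|
| Week 12 (Day 85) | 84 + 85 = 169 | 252 days | Weeks 28, 36, 44, 52 (4 of 6) |
| Week 24 (Day 169) | 168 + 85 = 253 | 168 days | Weeks 44, 52 (2 of 6) |
| Week 36 (Day 253) | 252 + 85 = 337 | 84 days | Week 52 (1 of 6) |
| Week 40 (Day 281) | 280 + 85 = 365 | 56 days | none |
| Week 48 (Day 337) | 336 + 85 = 421 | 0 | none |

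In the Week 40 row, the Week 52 target day lies exactly on the formula's last day. A Week 52 visit held later in its window (to Day 379) would fall outside.

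**Patients who leave the study soon after stopping.** If the last visit is 28 days after the last dose, the formula runs 84 − 28 = 56 days past it. The stated length differs, but no assessment is gained or lost.

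**Not countable.** The vital-sign rows are not in the available text of Table 6-1, so affected vital-sign visits cannot be counted. The documents do not give the expected number of early stoppers who remain.

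**The case against.** The best defence is that context points to the formula. It is the statement presented as the definition, its 84 days match both the exposure rule in SAP 2.4.1 and the treatment-emergent limit in SAP 2.8.1, and the data are labelled on-treatment. Patients who leave the study but keep follow-up visits 8 and 12 weeks after their last dose would end close to day 84 under either rule. All laboratory and vital-sign values are listed in any case, and the tables are descriptive.

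This limits the consequence but does not remove the conflict. SAP 2.4.1 takes the earlier of the two dates, but only for duration of exposure. Protocol 9.5.2 confines safety summaries to the on-treatment period without fixing its end for laboratory or vital-sign data.

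Three stronger readings are tempting and are not supported:

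- **That late CRP and ESR values drop out of the efficacy analysis.** SAP 2.7.2 does say of these endpoints "Further details are provided in Section 2.8.3", and 2.8.3 carries the restriction. But 2.8.3 names only hematology, clinical chemistry and urinalysis, and SAP 2.7 puts the secondary efficacy endpoints in the FAS. Where an efficacy table is to be cut after the last dose, as for remission over time in 2.7.2, the SAP says so. This merits a clarifying sentence only.
- **That early stoppers are mostly patients doing badly.** Patients who flare, miss remission or cannot follow the taper enter escape and continue blinded injections. Protocol 5.5 mentions disease progression as a possible reason to stop, but nothing shows that it predominates.
- **That Month X is an unfilled placeholder.** The section defines it as the last scheduled visit, which is Week 60. It is leftover wording.

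**Conclusion.** The section is wrong as written: it contains two rules that select different data, and the last-visit bullet would label values taken months off drug as on-treatment.

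The effect is confined to patients who stop injections at about Week 36 or earlier and are assessed more than 84 days after their last dose. For those followed to Week 60 it grows with earlier stopping, from one laboratory visit (last dose Week 36) to four of six (last dose Week 12). These counts assume visits on target days. The total effect on the tables cannot be computed without the number of such patients. Laboratory summaries, shift tables and vital-sign summaries are affected; the primary endpoint and the GO criteria in SAP 2.5.2 are not.

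**What to change.** 1. In SAP 2.1.1.4, replace the bullets and the formula with one rule: from first dose to the earlier of the last visit and the last dose plus 84 days. This follows the exposure rule in SAP 2.4.1 and uses the same 84 days as SAP 2.8.1. Later values stay in the listings already planned.
2. Reconcile the limit itself. SAP 2.8.1 counts adverse events as treatment-emergent to 84 days after the last dose; protocol 9.5.2 uses 20 weeks (140 days). Align them, or record the difference as a change in SAP section 4.
3. As a minor clarification, state in SAP 2.7.2 that CRP and ESR change from baseline uses all FAS data by visit and that the on-treatment restriction in 2.8.3 does not apply.

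The cost is SAP wording and programming only, with no new data. It should be done before database lock, so that the choice of rule cannot follow the results.
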